2. AIM AND OBJECTIVES

Pre-exposure antiretroviral prophylaxis comprising a daily dose of Truvada (Tenofovir/Emtricitabine) is a proven prevention strategy for same sex couples and discordant couples and now internationally recommended for individuals at substantial risk. The benefit of PrEP in high risk population groups significantly outweigh the potential threat of adverse events. The high risk population groups are MSMs, men in incarceration, commercial sex workers and adolescent girls and young women. Additional options for PrEP in young women through long acting antiretroviral (Dapivirine) prophylaxis in vaginal rings are also possible, but preclude use in pregnancy.

Truvada (the antiretroviral drug of choice for PrEP) is classified as a FDA pregnancy Category B antiretroviral. Pregnancy and lactation are distinct contraindications to initiate PrEP because of the limited evidence of its (Truvada) adverse effects on the child. Despite this classification, Truvada has been endorsed by the WHO to be used as part of a treatment combination in HIV infected pregnant women and to reduce motherto-child transmission of HIV. Arguably the benefits of Truvada, either as prophylaxis for prevention of mother to child transmission or as part of a treatment regimen for the mother, certainly outweigh the potential risk of adverse events (minimal) in this HIV infected population. But, do the benefits of Truvada as PrEP outweigh potential risk of adverse events in HIV uninfected pregnant women?

Because younger pregnant and lactating women are disproportionately at risk for HIV infection, a targeted intervention approach for HIV uninfected pregnant women aged between 18 and 24 years would yield a higher benefit:risk ratio. Therefore it would be ethically acceptable to demonstrate the safety of Truvada as PrEP in combination with current standard of care interventions to preventing sexually transmitted infections and HIV in this most vulnerable group of pregnant women. The Intervention Package would therefore include a daily dose of Truvada (TDF/FTC), risk reduction counselling, STI screening and treatment, inviting the sexual partner to receive HCT and referral for treatment and support if he tests HIV positive and condom promotion. The Control Group of young pregnant women will receive the above package minus the antiretroviral prophylaxis - Truvada (TDF/FTC).

2.1 Aim:

To explore the safety of Truvada when used as PrEP in combination with current recommendations for prevention of sexually transmitted infections and HIV in young women at substantial risk of HIV acquisition during pregnancy and lactation.

2.2 Primary Objective:

 To compare the frequency and seriousness of specific adverse events related to TDF/FTC in women and their children in Arm A (exposure to TDF/FTC) and Arm B (no exposure to TDF/FTC) during pregnancy until breastfeeding cessation.

2.3 Secondary Objectives:

- To estimate HIV incidence in women in ARM A with ARM B at delivery and at 18 months post-delivery.
- To determine the interdependency of adherence to a once daily oral TDF/FTC regimen and standard HIV prevention methods during pregnancy and postdelivery.
- To measure antiretroviral drug (TDF/FTC) level in women and their infants in association with adherence, safety and level of protection (plasma and breastmilk)
- To detect drug resistance among women who acquire HIV infection and correlate the treatment outcomes (after initiating immediate ARV treatment) with drug resistance
- To determine mother-to-child transmission of HIV among women who acquire incident infections during pregnancy and breastfeeding and the frequency of drug resistance in their infected babies
3. SETTING

The Umlazi Research Clinic is a well-established research facility, which hosts HIV prevention research with a particular focus on the prevention of mother-to-child transmission for the past 7 years. The facility is well equipped to conduct large cohort studies as well as smaller pharmacokinetic and safety studies. Umlazi, an urban and the third largest township in South Africa is located in the EThekwini District of KwaZulu-Natal. Umlazi is geographically divided into 26 sections and each section is alphabetically named as Section A or Section D or Section H, etc. Its estimated population of 1.6 million has access to a single regional hospital, Prince Mshiyeni. With a bed state of 1200, this institution provides a comprehensive, integrated health service with elements of preventive, promotive, curative and rehabilitative health care. Approximately 1100 births are recorded per month deliveries per month. Prince Mshiyeni is the referral hospital for 17 primary health care clinics in Umlazi. Busiest clinics in Umlazi are H, D, U and K clinics. The priorities of these clinics are maternal child chronic and care, **HIV/AIDS** and diseases.

Umlazi Township spans 26 sections and Umlazi Clinical Research Site is located on the grounds of Prince Mshiyeni Hospital.

3.1 Population at Risk

Pregnant women seek antenatal care at any of the 17 primary health care clinics and deliver at the Prince Mshiyeni Memorial District hospital. Women range in age between 16 and 40 years, and almost half (46%) of the women who deliver at the hospital are adolescents are young women (<25 years). Approximately 25% are primigravid and the average gestational age at first visit is 28 weeks, although 48% register prior to 20 weeks of gestation. The PHC clinics have an active PMTCT program. As prescribed in the National HIV treatment guidelines, pregnant women are offered HIV counselling and testing at their first antenatal visit. A serial HIV testing algorithm using Point of Care serological tests is implemented at all public health facilities. Women who are positive on the first POC test are immediately confirmed infected if the second POC test is also reactive. If pregnant women test negative on the first POC, they receive risk reduction counselling and informed of an opportunity to repeat the test 3 monthly during pregnancy and post-delivery.

In a maternity audit conducted at the District Hospital (PMMH) during a 3 month period in 2011 and 2014, 1732 (37.3%) and 2219 (38.7%) women were HIV positive among the 4644 and 5738 deliveries respectively. A third (34%) of the HIV infected pregnant women were <25 years and 52% of women who remained HIV negative by the time of delivery were between 18 and 24 years old.

In a cohort study conducted at a PHC clinic in Umlazi, 38% (548/1446) of antenatal attendees tested HIV positive and almost half (47%) of these women were <25 years

of age. The prevalence of Trichomonas, Chlamydia and Neisseria in pregnant women was 15.6%, 17.7% and 6.4% respectively. All three STIs were significantly more common in younger women <25yrs (17.2%, 21% and 8.6% vs 12.4%, 13.2% and 3.4% respectively) than older women. Among 636 pregnant women tested for HSV-2 shedding in cervical secretions, 52 (8.18%; 95%CI 6.22-10.65) women tested positive by DNA PCR. HSV-2 shedding was detected in 10.4% of HIV positive women and 6.7% of HIV negative women.

4. SELECTION OF PARTICIPANTS

4.1 Selection and Enrollment of Subjects

- 4.1.1 Inclusion Criteria
 - At least 18 years old.
 - Confirmed HIV-1 uninfected.
 - Willing to provide screening informed consent
 - Currently pregnant
 - Considered high risk for HIV infection
 - <25 years of age
 - Unprotected sex during pregnancy
 - HIV status of current sexual partner is positive or unknown
 - Results of HBV screening (HBsAg testing) available from specimen obtained within 30 days prior to entry
 - Plans to deliver in the study affiliated hospital
 - Has no plans to move residence outside of the catchment area during the 18 months following delivery

4.1.2 Exclusion Criteria

- HIV infected
- >24 years of age and <18 years of age
- The following laboratory values from a specimen obtained within 30 days prior to study entry:
 - Hemoglobin <11 g/dL
 - WBC < 1500 cells/mm³
 - ANC < 750 cells/mm³
 - Platelets < 100,000 cells/mm³
 - \circ ALT > 2.5 x upper limit of normal (ULN)
 - Estimated creatinine clearance of < 70mL/min using the Cockroft-Gault equation for women: {([140 – age (years)] x [weight (kg)]) ÷ [72 x serum Cr (mg/dL)]} x 0.85
 - Hepatitis B surface antigen (HBsAg) positive
- Participation in any other study
- In labour at onset or beyond
- Serious illness (including TB) and/or hospitalization
- Receipt of TB treatment within 30 days prior to study entry
- Fetus detected with serious congenital malformation (ultrasound not required to rule out this condition)
- History of documented structural or conduction heart defect
- Social or other circumstances which would hinder long-term follow-up, in the opinion of the site investigator
- Currently incarcerated
- Substance or alcohol abuse (a score of >8 on the WHO Alcohol Use).

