
Goal:

To explore the safety of Truvada when used as PrEP in combination with current recommendations for prevention of sexually transmitted infections in young women at substantial risk of HIV acquisition during pregnancy and lactation.

Study Population:

Pregnant women, at their first antenatal visit, HIV uninfected, without evidence of maternal or fetal complications and at substantially high risk for HIV infection.

Sample Size:

To compare the frequency and seriousness of adverse events in women receiving tenofovir/emtricitabine in pregnancy as opposed to women not receiving tenofovir/emtricitabine in pregnancy, we have based our sample size on the main clinically relevant pregnancy outcome. Although all pregnancy outcomes will be compared between the intervention (immediate PrEP) and control (deferred PrEP) groups, we based our sample size on the expected preterm delivery proportion among HIV uninfected women (South Africa 18.5%, Botswana 19%). A sample size of 421 in the Immediate PrEP group and 421 in the Deferred PrEP group (i.e. 842 in total) achieves 80% power to detect a non-inferiority margin difference between the group proportions of 0.075 or 7.5%. The reference group proportion (deferred PrEP) of pre-term delivery pregnancy outcome as a main clinically-relevant adverse event is 0.185 or 18.5%.

Study Design: An Open Label randomized control study. Pregnant women considered at high risk for HIV infection will be randomized to commencing PrEP in pregnancy with continued use throughout breastfeeding or deferred PrEP until breastfeeding cessation. Women in either group will receive the standard of care for prevention of HIV and other sexually transmitted infections.

		At ≥ 14 wks gestation				
\sim		Antepartum	Peripartum	Breastfeeding	Post BF cessation	
R a n	ARM A	PrEP (TDF/FTC) + SOC HIV Prevention	PrEP (TDF/FTC) + SOC HIV Prevention	PrEP (TDF/FTC) + SOC HIV Prevention	Option to Continue PrEP + SOC HIV Prevention	
d o m	OR					
i s e	ARM B	SOC HIV Prevention	SOC HIV Prevention	SOC HIV Prevention	Option to initiate PrEP + SOC HIV Prevention	
\sim /						

SOC – Standard of Care: Risk reduction counselling, STI screening and treatment, inviting the sexual partner to receive HCT and referral for treatment and support if he tests HIV positive and condom promotion.

Study Duration:

Mother: From the first antenatal visit in pregnancy until 18 months post-delivery.

Infant: From birth until 18 months of age.

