7.4 Screening

Screening and enrolment procedures will be completed within 14 days. Eligibility will be determined using a combination of biomedical and behavioural criteria. If a participant is not enrolled within 14 days of providing informed consent for screening, the participant will not be re-screened or enrolled. Screening will be completed in a step-wise manner. Firstly, potential participants will be invited to screen for the study and asked to provide informed consent for screening (Appendix 1). Potential study participants will be assigned a screening number, followed with a risk assessment (Appendix 2) and the first series of biomedical screening procedures including confirmation of HIV uninfected status. If both HIV test results are negative, the potential participant will be invited to continue with the screening process and will be asked to provide demographic information, locator information and blood for chemistry and haematological tests.

HIV Prevention Pregnancy Post-delivery Version 1.0

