7.21 Procedures for Assessing Safety

Participants will be asked one month after starting Truvada and at each subsequent scheduled visit whether they have had any admissions to hospital, or suffered from any significant illness that required medical attention. The site clinician will determine whether an illness meets the criteria for Serious Adverse Event (SAE) Reporting. SAEs will be reported to the UKZN BREC, Medicines Control Council and Department of Health. Participants will also be asked whether they have experienced any side effects.

Clinical assessments during pregnancy will be conducted as per the national guidelines for maternity care.

Maternal safety assessments during pregnancy and until 74 weeks study exit: All women will have bloods drawn for chemistry and haematological investigations at screening, enrolment, 2 weeks, 4 weekly until delivery, <72 hours of delivery, 2 weeks post delivery, 6 weeks, 10 weeks, 14 weeks and 4 weekly until 74 weeks (inclusive). Chemistry tests include liver function markers (ALT/AST/Phosporous), renal function (serum creatinine/urea/sodium/potassium), and bone density markers (serum calcium and magnesium).

Bone mineral content in the mother will be measured by DXA scan at 6 weeks postpartum, 6 months, 12 months and 18 months. Both Hip and Spine DXA scans will be done at above scheduled visits.

Within 72 hours of delivery, the participant with her maternity care record (MCR) will be reviewed by the study clinician. Fetal outcome in addition to other obstetric data will be extracted from the MCR. The following definitions will be used to document fetal outcome:

NON-VIABLE FETUS (MISCARRIAGE)

Less than 28 weeks* gestation and where there is no evidence of life at delivery. **STILL BIRTH** Gestational age of 28 weeks or more and where there is no evidence of life at delivery. **NEONATAL DEATH**** Death after a live birth whatever the duration of the pregnancy. **When the gestational age is not known, a legal weight cut-off of 1000 g is used.**

Maternal gestational age will be determined by clinical and obstetric assessments that will include an Ultrasound, measurement of symphysis fundal height and last menstrual date if known. Preterm delivery is defined as < 37 weeks. Moderate preterm delivery 32-35 weeks and severe preterm delivery <32 weeks.

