The New Ballard method will be used to assess gestational age of neonate. In addition, neonates will be determined small for gestational age (SGA), average for gestational age (AGA) and large for gestational age (LGA).

Fetal Growth:

Fetal monitoring will include fetal growth and an ultrasound for fetal abnormalities. For fetal growth monitoring, we would measure the symphsis fundus height at each study visit, plot on graph against gestational age and compare with 10th, 50th and 90th centiles and previous measurements. Any measurement <10th centile or failure to increase will be referred for an ultrasound for further fetal assessment.

Infants exposed to TDF/FTC either in-utero or during breastfeeding will have chemistry (serum creatinine) and haematological (complete blood count) at birth, 26 weeks (6 month), 50 weeks (12 months), and 72 weeks (18 months).

Infant Bone Growth:

DXA scans of the lumbar spine and whole body of infants will be performed at 6 weeks, 6 months, 12 months and 18 months to determine BMC and bone growth.

Clinical Examination of Infants:

Clinical examination of infants at birth will be conducted as per standard of care prescribed in the SA paediatric guidelines. This will include examination for physical abnormalities.

Physical examination of infants will include OFC, weight, and length to monitor growth and also include assessments for neurodevelopmental milestones at 6 weeks, 3 months, 6 months, 12 months and 18 months.

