Based on current data (maternal adverse events, maternal and infant bone mineral content depletion), all other adverse birth outcomes and maternal and infant adverse events can be housed within this sample size and will have smaller D as the relative prevalence decreases toward 0 i.e. narrower equivalence zones. Assuming a loss to follow-up of 5%, we would need 442 women in each group (884 in both arms combined) for the two year time frame of the study.

Outcome	n/N	Prevalence	Required sample size in each group for proposed equivalence trial	Total required sample size for proposed equivalence trial
Pre-term	1096/5916	18.5%	421	842
LBW	651/5916	11.0%	274	548
Small for GA	429/5916	7.3%	189	378
VLBW	141/5916	2.4%	64	128
Stillbirth	130/5916	2.2%	58	116

Main endpoint 1: sample size for safety in pregnancy for birth outcomes Prevalence adverse birth outcomes among HIV-ve (in descending order)

Based on a non-inferiority trial design: A sample size of 421 in the treatment group and 421 in the control group (i.e. 842 in total) achieves 80% power to detect a non-inferiority margin difference between the group proportions of 0.075 or 7.5%. The reference group proportion (pre-term delivery birth outcome) is 0.185 or 18.5%. The treatment group proportion is assumed to be 0.26 or 26% under the null hypothesis of inferiority. The power was computed for the case when the actual treatment group proportion is 0.185 or 18.5%. The test statistic used is the two-sided Z test (unpooled). The significance level of the test was targeted at two-sided 0.05 or 5%.

Secondary Endpoint

PASS 12 sample size software (Hintze, J. (2013). PASS 12. NCSS, LLC. Kaysville, Utah, USA. www.ncss.com) was to calculate this sample size. In order to show a 50% reduction in HIV infections, with significance level of 0.05 or 5% and 80% power, we would need to observe 66 HIV infections in total (44 in control arm [cumulative incidence of 12.72%] and 22 in the intervention arm [cumulative incidence of 6.36%]). This assumes an HIV incidence of 3 per 100 person years during the 6 months of pregnancy and 6 per 100 person years during the 18 months of breastfeeding [9]. Based on these assumptions, we would require 334 subjects in group or 668 in total. Assuming a loss to follow-up of 10%, we would need to increase this to 346 women in each group (692 in both arms combined) for the two year time frame of the study.

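### No upper gestational-age limit at randomisation and no at-risk set for preterm delivery, so women already at 37 weeks dilute the non-inferiority comparison (a small effect unless they approach 10% of the trial)

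*Combined protocol and SAP*

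**What the plan says.** **Entry.** Section 4.1.1 requires "Currently pregnant", and section 4.1.2 excludes women "In labour at onset or beyond". The Study Design schema in the synopsis adds a floor, "At ≥ 14 wks gestation". Pre-screening (7.3) has no gestational criterion beyond the absence of major obstetric complications. Section 3.1 reports that in the source population "the average gestational age at first visit is 28 weeks". Section 7.4 says "Screening and enrolment procedures will be completed within 14 days".

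**Endpoint.** Section 7.21 says "Preterm delivery is defined as < 37 weeks", with no condition on gestation at entry. It dates the pregnancy by ultrasound, fundal height and last menstrual period. It then adds "The New Ballard method will be used to assess gestational age of neonate", without saying which dating classifies preterm delivery.

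**Analysis.** Section 10.3 sizes the trial at 421 per arm for 80% power, with a control rate of 18.5%, a 7.5-point margin and an unpooled Z test at two-sided 5%. It states: "The treatment group proportion is assumed to be 0.26 or 26% under the null hypothesis of inferiority". Section 10.4 defers full details to a later SAP but presents itself as the description of the primary safety analysis. That analysis is intention-to-treat in everyone randomised. A per-protocol analysis is added, but it is not defined by gestation.

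**The concern.** By baseline dating, a woman randomised at 37 weeks 0 days or later cannot deliver preterm, whatever her arm. With up to 14 days between screening and enrolment, this can include a woman screened at 35 weeks. She adds to the denominator of both arms and to the numerator of neither.

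If PrEP raises preterm risk among women who can still deliver preterm, the absolute difference over all randomised women is smaller than the difference among those at risk, while the margin stays at 7.5 points. The error is therefore towards declaring PrEP acceptable. Randomisation balances the late entrants between arms but does not remove the dilution.

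The unsettled dating rule adds ambiguity. If the neonatal assessment decided the endpoint, a woman dated at 37 weeks when randomised could still be recorded as preterm.

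**Working it through.** **Inputs.** From 10.3: control rate 0.185, margin 0.075, one-sided error 0.025 (two-sided 5%), power 80%, unpooled variance, 5% loss. The share f of each arm randomised at 37 weeks 0 days or later is **not in the documents**; 2%, 5% and 10% are assumed (about 8, 21 and 42 women per arm of 421).

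**The plan's own figure.** n = (1.960 + 0.842)² × 2 × 0.185 × 0.815 / 0.075² = 420.8, so 421 per arm. This matches, and power at 421 is 80.0%.

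**Chance of declaring non-inferiority.** P = Φ[(0.075 − (p1 − p0))/SE − 1.96], with SE = √{[p0(1 − p0) + p1(1 − p1)]/421}. The true excess among at-risk women is set to exactly 7.5 points.

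*Reading A: 18.5% is the overall control rate.* It comes from 1096/5916 births with no stated restriction by gestation at booking, so this is the main reading. Then p0 = 0.185 and p1 = 0.185 + 0.075(1 − f). Example at f = 5%: p1 = 0.25625, SE = 0.02848, (0.075 − 0.07125)/0.02848 = 0.132, and Φ(0.132 − 1.96) = 0.034.

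*Reading B: 18.5% is the at-risk rate.* Then p0 = 0.185(1 − f) and p1 = 0.26(1 − f).

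| f | At-risk excess tolerated, 7.5/(1 − f) | P, reading A | P, reading B |
|---|---|---|---|
| 0 | 7.5 points | 2.5% | 2.5% |
| 2% | 7.7 | 2.8% | 2.8% |
| 5% | 7.9 | 3.4% | 3.4% |
| 10% | 8.3 | 4.5% | 4.6% |

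Under reading A, P reaches 4% at f of about 8% and 5% at about 12%. Simulation of reading A (400,000 trials per point) gave 2.56%, 2.82%, 3.40% and 4.53% for the four rows.

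**Restricting to women randomised before 37 weeks 0 days.** The at-risk excess then equals the margin, so P returns to 2.5% at every f. With 421 randomised per arm, the set has 421(1 − f) women. Power under equal arms:

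| f | Reading A, rate 0.185/(1 − f) | Reading B, rate 0.185 |
|---|---|---|
| 2% | 78.6% | 79.2% |
| 5% | 76.4% | 78.0% |
| 10% | 72.4% | 75.8% |

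**Numbers randomised to leave 421 at-risk women after 5% loss.** 421/[0.95(1 − f)] = 452.2, 466.5 and 492.4, so 453, 467 and 493 per arm. The same division at f = 0 gives 444; the plan's 442 is 421 × 1.05. Under reading B, 421 at-risk women give 80% power. Under reading A the at-risk rate is above 18.5%, and 80% needs 428, 438 or 456 at-risk women.

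**The case against.** The strongest objection is that the stated test is not broken. Against the protocol's literal null for all randomised women (26% versus 18.5%), one-sided error stays at 2.5%, and with equal arms there is no bias. The effect in everyone randomised is a coherent intention-to-treat quantity. This stands: the inflation concerns only the question of harm among women who can still deliver preterm. That is nevertheless the question a preterm safety comparison is meant to answer, and 10.4 itself recognises that smaller differences are not conservative in non-inferiority testing.

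Second, f is unknown and probably small. The maternal schedule heads the enrolment visit with 14 weeks, and 10.3 assumes 6 months of pregnancy follow-up. This also stands and is why the point is minor. Section 3.1 cannot settle it. A mean of 28 weeks with 48% booking before 20 weeks would put the other 52% above (28 − 0.48 × 20)/0.52 = 35.4 weeks on average. Those figures look strained and cover attendees of all ages, so they show only that entry well after 14 weeks occurs.

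Third, the preterm definition follows directly after the obstetric dating methods in 7.21, which suggests that those classify it. That is the natural reading, but it is not stated.

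Fourth, late entrants still inform renal, bone and infant-growth outcomes, so open entry can be reasonable. Agreed. An entry ceiling below 37 weeks would leave 421 unchanged but lose those women; an analysis-set rule keeps them.

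Finally, a woman entering at 36 weeks 6 days stays in the restricted set with almost no time at risk. The remedy is therefore partial.

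**Conclusion.** The concern holds and is minor. The plan has neither an upper gestational-age limit at randomisation nor an at-risk set for its sizing outcome, and the resulting dilution favours non-inferiority. The cost is roughly 0.3, 0.9 or 2 percentage points of extra one-sided error at an assumed f of 2%, 5% or 10%. It matters materially only if f nears 10%. The result hardly depends on whether 18.5% is read as the overall or the at-risk rate. It rests on an assumed f, on a true excess of 7.5 points among at-risk women, and on baseline dating classifying the endpoint.

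**What to change.** In 10.4 or the SAP, before outcome data are seen:

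- Define the main preterm analysis set as women randomised before 37 weeks 0 days. Use the gestational age fixed at screening, where an ultrasound is already scheduled, carried forward to the randomisation date. This is a pre-randomisation variable, so the comparison stays randomised.
- State that the same baseline dating classifies preterm delivery.
- Keep the all-randomised result as a sensitivity analysis, and report by arm the number randomised at 37 weeks or later.
- Adjustment for gestational age at randomisation may add precision, but it does not restore the short exposure of women entering just before 37 weeks.

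In 10.3, state that the 421 per arm refers to at-risk women, and whether 18.5% is the at-risk or the overall rate, since 421 at-risk women give 80% power only in the former case.

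The cost is a few sentences, no new data and the modest power loss shown in the working. Enlarging the trial to recover that power is optional.
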